#### 2.3. Hypotheses

Primary Hypotheses (each is considered independent)

- 1. Light Scattering
  - a. The Test lens (in the absence of an additional UV/HEV light source) will be statistically lower than the Control lens with respect to light scattering as measured using the two-point light threshold instrument.
  - b. The Test lens (in the presence of an additional UV/HEV light source) will be statistically lower than the Control lens with respect to light scattering as measured using the two-point light threshold instrument.

- 2. Haloes
  - a. The Test lens (in the absence of an additional UV/HEV light source) will be statistically lower than the Control lens with respect to halos. This is measured using the halometer instrument.
  - b. The Test lens (in the presence of an additional UV/HEV light source) will be statistically lower than the Control lens with respect to halos. This is measured using the halometer instrument.
- 3. Starbursts
  - a. The Test lens (in the absence of an additional UV/HEV light source) will be statistically lower than the Control lens with respect starbursts as measured using the halometer instrument.
  - b. The Test lens (in the presence of an additional UV/HEV light source) will be statistically lower than the Control lens with respect starbursts as measured using the halometer instrument.

Secondary Hypotheses (each is considered independent)

- 1. The Test lens (in the absence of an additional UV/HEV light source) will be statistically lower than the Control lens with respect to photostress recovery time (seconds) as measured using the optical bench instrument.
- 2. The Test lens (in the absence of an additional UV/HEV light source) will be statistically higher than the Control lens with respect to disability glare threshold as measured using the optical bench instrument.
- 3. The Test lens (in the absence of an additional UV/HEV light source) will be statistically lower than the Control lens with respect to discomfort glare (eyelid squinting) as measured using the optical bench instrument.
- 4. The Test lens (in the absence of an additional UV/HEV light source) will be statistically higher than the Control lens with respect to chromatic contrast threshold than as measured using the optical bench instrument.

Other Hypotheses

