## 14.4. Level of Statistical Significance

Each primary and secondary hypothesis will be tested individually using a type I error rate of 5%.

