# 14.5. Primary Analysis

# Light Scattering (Two-point Light Spread Function)

This is defined as the minimum distance (mm) that two points of light are completely distinct. This threshold will be analyzed by a linear mixed model. Sequence of lens wear, lens type, age group, dominant eye and the interaction between lens type and age group will be included in the model as fixed effects. An appropriate covariance structure will be used to model the residual errors between measurements between eyes within a subject. The variance-covariance structure will be selected based on the finite-sample corrected Akaike's Information Criterion Corrected (AICC). The structure that returns the lowest AICC will be deemed the most appropriate structure. Covariance structures under consideration include:

- Unstructured (UN)
- Compound Symmetry (CS)
- Heterogeneous Compound Symmetry (CSH)

Heterogeneous covariance structures across lens type may be considered if necessary. The Kenward and Roger method (Kenward and Roger, 1997) will be used for the denominator degrees of freedom.

Comparisons between lenses (Test inactivated vs Control and Test activated vs Control) will be carried out using 2-sided 95% confidence intervals constructed for the least-square mean (LSM) difference (Test – Control). Statistically significantly lower differences of the Test lens relative to the Control lens will be concluded if the upper limit of the 95% confidence interval is below 0. If the interaction between lens type and age is significant then comparisons between lenses will be made within age group.

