## Starburst

Starbursts will be quantified by the diameter of the light's lateral spread. A calibrated custommade micrometer (two sides with reverse threading) will be used to spread two posts out from a central mid-point). Those posts can then be used to define the outer boundaries of the starburst image (i.e. the diameter). The diameter of the light's lateral spread will be analyzed and tested in the same manner as described for light scattering above.

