## Halos

Halos will be quantified by the diameter (mm) of outer edges of the halo image and is measured using the same micrometer as for starbursts and light scattering. The diameter will be analyzed using the same model as described for light scattering.

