#### Disability Glare Threshold (Change in log relative energy level)

Glare disability threshold (GDT) (change in log relative energy level) will be evaluated by exposing subjects to various intensity of a white-light annulus (10-geg diameter) and will be quantified by the log relative energy level necessary to obscure a central target.

GDT will be analyzed and tested in the same manner as described for PSRT.

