#### Discomfort Glare (change in palpebral fissure height (mm))

Glare discomfort (GD) will be evaluated by squint response of the extraocular muscles and by a subjective questionnaire regarding the patients' comfort. Squint response will be captured by using a high-resolution camera for each subject eye. The resultant videos will then be analyzed as still frames. Squint response will be quantified as the calculated ratio of the height of the palpebral fissure under normal light conditions compared to maximal squint produced during the Photostress exposure. GD will be analyzed in the same manner as described for PSRT.

Comparisons between lenses will be carried out using 2-sided 95% confidence intervals constructed for the least-square mean (LSM) difference (Test – Control). Statistically significantly higher differences of the Test lens relative to the Control lens will be concluded if the lower limit of the 95% confidence interval is above 0. If the interaction between lense type and age is significant then comparisons between lenses will be made within age group.

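### Does switching to within-age comparisons after a significant lens-by-age interaction undermine the error rate of the lens comparisons?

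*Combined protocol and SAP*

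**What the plan says.** In section 14.5 (Light Scattering), the mixed model contains lens type, age group and their interaction. Each of the two comparisons, Test inactivated against Control and Test activated against Control, uses a two-sided 95% interval for the least-square mean difference. A significantly lower value for Test "will be concluded if the upper limit of the 95% confidence interval is below 0". The paragraph ends: "If the interaction between lens type and age is significant then comparisons between lenses will be made within age group".

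The rule reaches nearly every endpoint:

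- Starburst diameter "will be analyzed and tested in the same manner as described for light scattering above".
- For halos the wording covers the model only: "The diameter will be analyzed using the same model as described for light scattering". The switch presumably follows.
- In section 14.6 the sentence is written out for photostress recovery and again for discomfort glare ("If the interaction between lense type and age is significant then comparisons between lenses will be made within age group").
- For disability glare, "GDT will be analyzed and tested in the same manner as described for PSRT". Heterochromatic contrast is tied to discomfort glare in the same way.

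On the error rate, section 14.4 says: "Each primary and secondary hypothesis will be tested individually using a type I error rate of 5" percent. The hypotheses in section 2.3 are one-directional and name no age group; for example, the Test lens "will be statistically lower than the Control lens with respect to halos".

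**The concern.** When the interaction is significant, one comparison per hypothesis appears to become two, each at the full 95% level with no adjustment. Two things are left open. Section 14.4 sets a level for the primary and secondary hypotheses, and the interaction is not one of them. Nor does the plan say whether an age-free hypothesis is confirmed by success in one age group or only by success in both.

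Two consequences would follow. A trial with no lens effect could get an extra chance to claim benefit through an age subgroup. And if one age group met the criterion and the other did not, the same data could be written up as confirming the hypothesis or as failing to, with the choice made after the results were known.

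**Working it through.** **Inputs from the documents.** 5% per hypothesis (14.4). Two-sided 95% interval, with success on one side only (14.5, 14.6). Age groups of 40 ±3 and 20 ±3 (4.3). Three lens conditions for the primary endpoints, so a joint interaction test has 2 degrees of freedom; two conditions for the secondary endpoints, so 1 degree of freedom (2.2).

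**Assumptions.** Normal within-subject Test-Control differences with equal variance in the two age groups, pooled on 40 + 20 − 2 = 58 degrees of freedom. Interaction tested at 5%. The overall difference weights the age groups either equally (the usual default for least-square means) or by observed size; ranges span the two. Rates are from simulation, 1,000,000 null trials per setting.

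**1. The plan's own figure.** One comparison with a two-sided 95% interval and a one-sided conclusion gives a false-benefit rate of 5% / 2 = 2.5%.

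**2. Reference point.** If the two within-age comparisons were always used and either could succeed, the rate would be 1 − 0.975² = 4.94%.

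**3. The switch, secondary endpoints, either group counting.** Under no effect the interaction is falsely significant in 5% of trials, and at least one age group then meets the criterion in about 35.5% of them. With observed-size weights the overall test is nearly unrelated to the age difference, so the rate is close to 0.05 × 0.3545 + 0.95 × 0.025 = 0.0177 + 0.0238 = 0.0415. Simulation gives 4.1%, and 4.0% with equal weights.

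**4. The switch, primary endpoints, either group counting.** With the 2-degree-of-freedom interaction test the rate is 3.5-3.6%. At the quota limits (43/17 and 37/23) it is 3.4-3.6%.

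**5. Both groups required after a significant interaction.** The rate is 2.2-2.4% across primary and secondary endpoints, so there is no inflation.

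**6. Size of the excess.** 3.5 − 2.5 = 1.0 point at the low end and 4.1 − 2.5 = 1.6 points at the high end, under the either-group reading only. For scale, the plan openly leaves six primary hypotheses unadjusted. If they were independent, the chance of at least one false benefit would be 1 − 0.975⁶ = 14.1%.

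**7. What the alternatives would cost.** Chance of concluding benefit on a primary endpoint, with assumed effects, the interaction at 5% and correlation 0.5 between the two lens contrasts:

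| Assumed true effect | Switch, either group counts | Overall test only | Switch, both groups required |
|---|---|---|---|
| 0.5 SD, younger only (equal weights) | 70% | 43% | 28% |
| 0.6 SD, older only (equal weights) | 72% | 58% | 20% |
| 0.6 SD, older only (observed-size weights) | 66% | 33% | 14% |

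With a common effect of 0.390 SD and equal weights, the overall test has 80% power and the both-groups rule 77%. Each alternative therefore loses detection in the situation the switch is meant for, a lens effect that differs by age.

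**The case for a change.** The strongest argument for a change does not depend on simulation. The trigger is written down in advance but the conclusion is not. With a 0.5 SD effect in younger subjects only, equal weights and a 1-degree-of-freedom interaction test at 5%, success is 71% if either group counts and 29% if both must, so the unstated rule matters. A sentence would close the gap at no cost in subjects or data. Section 14.4, read literally, also does not cover the interaction. At 10% the either-group rate would be 4.0-4.2% (primary) and 4.6-4.8% (secondary); at 15% it would be 4.4-4.6% and 4.9-5.2%. A Bonferroni split of the within-age tests would not fully repair this, leaving 3.0-3.2% and 3.3-3.5% at a 5% interaction level.

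Part of this stands: the interaction level and the combining rule are absent. The rest is weaker. Section 14.4 names only one significance level, so 5% is the natural reading of "significant", and nothing in the documents points to 10% or 15%. Counting false results in both directions would roughly double the rates, but the plan draws no conclusion from a difference in the wrong direction. The either-group rule that produces all the inflation is also an addition to the text. Comparisons made within age group lead most directly to a separate statement for each group, and a reader who sees both intervals is not misled about which group benefited.

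**Conclusion.** No change follows. The omission is real, but analysts would fill it sensibly by testing the interaction at 5% and reporting an age-specific conclusion for each group. Under the least favourable combining rule, the excess at a 5% interaction level is 1.0 to 1.6 percentage points over 2.5% and stays under the 5% set for each hypothesis; if both groups are required it disappears. Making the overall difference the sole test, or requiring both groups, is a trade-off on which statisticians reasonably differ, because an average over age groups is hard to interpret when the interaction is significant. The stakes are also modest: section 14.2 says the sample size had no power basis and that the data will inform the sizing of follow-up studies. These figures rest on equal variances, age groups within the planned quotas and the 5% interaction level. A more liberal level would raise the either-group rates, in the extreme case slightly past 5% for secondary endpoints.

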## Starburst

Starbursts will be quantified by the diameter of the light's lateral spread. A calibrated custommade micrometer (two sides with reverse threading) will be used to spread two posts out from a central mid-point). Those posts can then be used to define the outer boundaries of the starburst image (i.e. the diameter). The diameter of the light's lateral spread will be analyzed and tested in the same manner as described for light scattering above.

## Halos

Halos will be quantified by the diameter (mm) of outer edges of the halo image and is measured using the same micrometer as for starbursts and light scattering. The diameter will be analyzed using the same model as described for light scattering.

## 14.6. Secondary Analysis

## Photostress Recovery Time (Seconds)

Photostress recovery time (PSRT) will be evaluated by exposing subjects to an intense light source (10-deg circular broad-band white at ~4.5 log Tds) and will be quantified as the time necessary to regain site of the grating after exposure.

PSRT will be analyzed using a linear mixed model. Sequence of lens wear, lens type, age group dominant eye and all the interaction between lens type and age group will be included as fixed

effects. An appropriate covariance structure will be used to model the residual errors between measurements between eyes within a subject. The variance-covariance structure will be selected based on the finite-sample corrected Akaike's Information Criterion Corrected (AICC). The structure that returns the lowest AICC will be deemed the most appropriate structure. Covariance structures under consideration include:

- Unstructured (UN)
- Compound Symmetry (CS)
- Heterogeneous Compound Symmetry (CSH)

Heterogeneous covariance structures across lens type may be considered if necessary. The Kenward and Roger method (Kenward and Roger, 1997) will be used for the denominator degrees of freedom.

Comparisons between lenses will be carried out using 2-sided 95% confidence intervals constructed for the least-square mean (LSM) difference (Test – Control). Statistically significantly lower differences of the Test lens relative to the Control lens will be concluded if the upper limit of the 95% confidence interval is below 0. If the interaction between lens type and age is significant then comparisons between lenses will be made within age group.

#### Disability Glare Threshold (Change in log relative energy level)

Glare disability threshold (GDT) (change in log relative energy level) will be evaluated by exposing subjects to various intensity of a white-light annulus (10-geg diameter) and will be quantified by the log relative energy level necessary to obscure a central target.

GDT will be analyzed and tested in the same manner as described for PSRT.

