#### The background

The background channel will be manipulated to produce either an annulus (for GDs) or a three-degree background field (for GDc and PR). For the HCT test, the same three-degree background will be filtered through a 460 nm interference filter (half-power bandwidth = 8 nm; Edmund Optics; Barrington, NJ) in order to produce a monochromatic field. Xenon was selected as the light source because it has the characteristic broad band emission spectrum (as assessed by the SpectraScan colorimeter) with a CIE chromaticity of u' = 0.25, v' = 0.53. Xenon is widely regarded as a good match for sunlight. For example, in a study of 26 solar simulators, the authors noted that xenon-arc light sources match the most accurately. The xenon spectrum that will be produced by this system is shown in Figure 4 as compared to mid-day sunlight.

JJVC CONFIDENTIAL

[figure not shown]

Figure 4: The xenon (dark line) compared to noon day sun light (red line). The line in red is taken from the NASA solar spectrum measured at the earth's surface  and adjusted along the ordinate with respect to the xenon source that will be used in this study.

JJVC CONFIDENTIAL

	Psychophysical Testing A: Photostress / Glare / Chromatic Contrast		
Т	The psychophysical tests described in Steps 1-4 below may occur in any order. No additional UV/HEV activation light source will be used.		
Step	Procedure	Details	
1	Glare Disability (GDs)	The target stimulus will be presented for 2 seconds on and 1 second off to reduce the chances that subjects will habituate to the stimulus. A second channel will provide an annulus with an approximately 11-degree inner diameter and 12-degree outer diameter, as shown below.	
		Before each trial, the annulus will be set at a level well below that which would cause the target stimulus to be veiled. The experimenter will then adjust, via the neutral-density wedge, the intensity of the annulus until the target stimulus is no longer visible. Participants will indicate that the target has been veiled by pressing a buzzer.	
		The experimenter increases the intensity of light scattering within the subjects' test eyes until they cannot effectively see. Unlike the photostress bleach which is set and standard, the intensity is varied in this test, and hence, so is the aversiveness of the dependent variable. This measurement has been conducted successfully, repeatedly, in the past 	

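### Section 14.6 has no rule for concluding that Test is higher on disability glare, and its discomfort-glare rule conflicts with the hypothesis on a scale that is not fixed

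*Combined protocol and SAP*

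**What the plan says.** **Disability glare.** Secondary hypothesis 2 in Section 2.3 states that Test "will be statistically higher than the Control lens with respect to disability glare threshold as measured using the optical bench instrument". In the glare disability step of Section 7.2 (Psychophysical Testing A), the experimenter adjusts "the intensity of the annulus until the target stimulus is no longer visible". Section 14.6 says the endpoint "will be quantified by the log relative energy level necessary to obscure a central target", and then that "GDT will be analyzed and tested in the same manner as described for PSRT". The decision sentence under photostress recovery time is: "Statistically significantly lower differences of the Test lens relative to the Control lens will be concluded if the upper limit" of the 95% interval for Test – Control is below 0. No other conclusion is stated there.

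**Discomfort glare.** Secondary hypothesis 3 states that Test "will be statistically lower than the Control lens with respect to discomfort glare (eyelid squinting"). Section 14.6 first says the endpoint is analysed as photostress recovery time, then gives it a decision sentence of its own: "Statistically significantly higher differences of the Test lens relative to the Control lens will be concluded if the lower limit" is above 0. The heading of that subsection, "Discomfort Glare (change in palpebral fissure height (mm", describes a change in mm. The text below it, and the glare discomfort step in Section 7.2, instead define a ratio that compares normal fissure height with maximal squint. Section 7.2 labels that ratio the degree of squint. The synopsis calls the endpoint a threshold.

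**Chromatic contrast.** Section 14.6 tests this endpoint in the same way as discomfort glare. Secondary hypothesis 4 expects Test higher.

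**The concern.** A decision rule should be able to confirm the hypothesis it serves. For disability glare it cannot: a better lens raises the threshold, and the only written conclusion is that the threshold is lower. For discomfort glare, the wording of the rule is opposite to that of the hypothesis. Whether it is also opposite in substance depends on a scale that the plan defines inconsistently.

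The interval would still show a disability-glare benefit. To conclude hypothesis 2 from it, however, would depart from the written rule, and Section 14.10 requires any such change to be documented and justified in the study report. Unless the wording is corrected first, that would be done with the data in hand. For discomfort glare, the choice of scale decides whether a significantly higher result means less squinting or more. Site staff who collect the data know the lens assignment (Section 5.2) and the discomfort-glare value is calculated at the site (Section 15.1), which is a further reason to fix scale and direction beforehand.

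**Working it through.** The plan states no power, effect size or SD for these endpoints (Section 14.2 reports no power calculation), so there is no figure to reproduce.

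**1. Direction of hypothesis against direction of rule**

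| Secondary endpoint | Section 2.3 | Written rule in 14.6 (Test – Control) | Agree? |
|---|---|---|---|
| Photostress recovery | Test lower | lower if upper limit < 0 | yes |
| Disability glare | Test higher | lower if upper limit < 0 (by reference) | no |
| Discomfort glare | Test lower | higher if lower limit > 0 | no |
| Chromatic contrast | Test higher | higher if lower limit > 0 (by reference to discomfort glare) | yes |

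For disability glare the orientation is clear. The measurement is the annulus energy at which the target disappears, so a larger value means more glare tolerated. Hypothesis 2 therefore has the right direction, and the borrowed rule has the wrong one.

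**2. What the disability-glare mismatch does (illustration)**

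Inputs: n = 60 completers (Section 14.2) and a two-sided 95% interval (Section 14.6). Assumption: a true benefit of d SDs of the paired difference. I approximate the mixed model by a paired t-test, so T is noncentral t with 59 df and noncentrality d√60. The matching rule is met when T > t(0.975, 59), and the written rule when T < –t(0.975, 59).

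| d | Matching rule (lower limit > 0) | Written rule (upper limit < 0) |
|---|---|---|
| 0.1 | 0.12 | 0.003 |
| 0.2 | 0.33 | 2.5 × 10⁻⁴ |
| 0.3 | 0.63 | 1.1 × 10⁻⁵ |
| 0.4 | 0.86 | 2.7 × 10⁻⁷ |
| 0.5 | 0.97 | 3.9 × 10⁻⁹ |

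At d = 0.3, the matching-rule probability runs from 0.58 to 0.67 for n from 54 (assumed) to 66 (maximum enrolment).

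**3. Sign of a discomfort-glare benefit on each possible scale**

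Assumed heights: normal 10 mm; maximal squint 5 mm with Control and 6 mm with Test, so Test squints less and is better.

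| Scale | Test – Control | Does the written "higher" rule fit a benefit? |
|---|---|---|
| normal / squint | 10/6 – 10/5 = –0.33 | no |
| squint / normal | 6/10 – 5/10 = +0.10 | yes |
| normal – squint, mm | (10 – 6) – (10 – 5) = –1 | no |
| squint – normal, mm | (6 – 10) – (5 – 10) = +1 | yes |

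The rule fits on two scales and is reversed on two. The defined ratio names normal height first and is labelled degree of squint, which points to normal / squint. On that scale larger means more squinting, and the rule is reversed. With normal height 8–11 mm, Control squint 4–6 mm and Test 1 mm wider, the normal / squint difference runs from 8/7 – 8/6 = –0.19 to 11/5 – 11/4 = –0.55. Its sign therefore does not depend on the heights chosen, once that orientation is accepted.

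**The case against.** The strongest reply is that Section 2.3 already fixes the direction for disability glare, Section 14.4 tests each hypothesis individually at 5%, and the borrowed text supplies the model, the contrast and a two-sided interval. Together these imply one way to conclude hypothesis 2: lower limit above 0. On this view only a sentence is missing, and no data-driven choice of direction is open. That is a fair account of the intent, but the plan says disability glare is tested, not just modelled, as photostress recovery is, and that brings in the "lower" conclusion. The authors did write a "higher" rule and attached it to discomfort glare and chromatic contrast instead. The text as it stands is wrong, not merely silent.

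On discomfort glare, reversal is not proved: no formula or numerator is given, and squint / normal, or a signed squint-minus-normal change, would make the rule fit. That stands. It limits the claim to a conflict that the text cannot resolve, with reversal the more literal reading.

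The probabilities in the first illustration compare the right tail with the wrong one, so the written rule must score near zero. They show the consequence of the wording, not a loss of power or a change in error rate. Chromatic contrast is not a defect today; it matters only because of how the correction is made.

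These are secondary endpoints. The written primary rules for light scattering and starbursts match their hypotheses. The halo paragraph in Section 14.5 cites only the same model, so its rule has to be read across from light scattering.

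**Conclusion.** The concern holds. For disability glare, confidence is high: no written rule can conclude hypothesis 2, and the rule given by reference points the other way. With 60 pairs and a true benefit of 0.2 to 0.5 SD, it would be met with probability below 0.001, against 0.33 to 0.97 for a matching rule. These figures rest on assumed effects and a paired-t approximation. For discomfort glare, confidence is high that hypothesis, rule and scale do not agree, and moderate that the rule is reversed, since that depends on reading the ratio as normal divided by squint. Estimates, intervals and the primary analyses are not affected. It should be fixed.

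**What to change.** Amend Section 14.6 before database lock:

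- **Disability glare:** replace the reference to photostress recovery with its own rule. Test is concluded higher if the lower 95% limit of Test – Control is above 0.
- **Discomfort glare:** state one unit and one orientation, with the numerator or the order of subtraction, and match the rule to hypothesis 3. If the ratio is normal height divided by maximal-squint height, Test is concluded lower if the upper limit is below 0. Bring the mm heading and the synopsis label into line.
- **Chromatic contrast:** write out the "higher" rule (lower limit above 0) here instead of referring to discomfort glare. Otherwise, correcting discomfort glare alone would reverse a rule that is now right.

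The cost is SAP wording only. No data, procedure or sample size changes.
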